4.2. Final Analyses

The final analysis will be performed after the last patient has the week 16 efficacy assessment.

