As the length of treatment for any patient will depend on the efficacy and toxicity of the treatment, the duration of follow-up will vary among patients. Consequently, there will be no imputation for missing data. Answers such as "Not applicable" and "Not evaluable" are not considered to be missing data and should be displayed as such. Subjects with unknown or missing best response will be assumed to be non-responders and will be included in the denominator when calculating percentages.

Subjects with the designation of treatment relationship for adverse events (AEs) and serious adverse events (SAEs) missing will have the worst case assumed to impute the relationship: if the relationship to study treatment is missing, it will be assumed to be "Yes" for summary of drug-related AE or SAE.

In the event that the study is prematurely discontinued, all available data will be listed and a review will be carried out by the study team to assess which statistical analyses are still considered appropriate.

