9.2.4. Duration and Elapsed Time

Durations (e.g., the duration of an adverse event, duration of exposure, etc.) are calculated as the stop date minus the start date plus one.

For elapsed time (e.g., the time since initial diagnosis):

- If the reference date is on or after the event date, then the elapsed time is the reference date minus the event date + 1.
- If the reference date is before the event date then the elapsed time is the reference date minus the event date.

When reporting time to event (TTE) durations such as duration of response (DOR) in months, divide the number of days by 30.4375; to report in weeks divide the number of days by 7; to report in years divide the number of days by 365.25. These algorithms for time to event return decimal numbers, and ignore the actual numbers of days in the months or years between start date and stop date. The "year" used in these algorithms is 365.25 days long, and the "month" is one twelfth of that year.

For converting all other durations (e.g. duration of adverse events, duration of exposure, age) to weeks, months or years use the following:

- To report the duration in weeks divide the number of days by 7.

- To report the duration in months use:

$$(\text{YEAR}(\text{stopdate}+1) - \text{YEAR}(\text{startdate})) * 12 + (\text{MONTH}(\text{stopdate}+1) - \text{month}(\text{startdate}) - 1) + (\text{DAY}(\text{stopdate}+1) \geq \text{DAY}(\text{startdate}))$$

- To report the duration in years use:

$$\text{intck}(\text{'year'}, \text{startdate}, \text{stopdate}+1) - (\text{month}(\text{stopdate}+1) < \text{month}(\text{startdate}) \text{ or } (\text{month}(\text{stopdate}+1) = \text{month}(\text{startdate}) \text{ and } \text{day}(\text{stopdate}+1) < \text{day}(\text{startdate})))$$

The algorithms above for age and duration return whole numbers for months and years, accurately accounting for the actual numbers of days in the months or years between the start date and the stop date.

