9.2.5. Imputation of Partial Dates

Imputed partial dates will not be used to derive study day, duration (e.g. duration of adverse events), or elapsed time variables. In addition, imputed dates are not used for deriving the last contact date in overall survival analysis dataset (ONCSURV).

With the exception of new anti-cancer start date (NEWCTXDT) on the Oncology time to event analysis dataset (ONCTTE) [,][and] exposure end date (EXENDT) on the Exposure analysis dataset, [and other variables and datasets] imputed dates will also not be stored on datasets.

Imputed dates will not be displayed in listings. However, where necessary, display macros may impute dates as temporary variables for the purpose of sorting data in listings only. In addition partial dates may be imputed for 'slotting' data to study time periods (Section 9.3) or for specific analysis purposes as outlined below.

The partial date imputation will follow Analysis Data Model (ADaM) conventions. The ADaM approach is to populate the numeric date variables with the imputed date and add a flag variable to the dataset that indicates the level of imputation. The flag variable can contain the values: blank, 'D', 'M', 'Y'.

Blank: indicates that no imputation was done

D='Day': indicates that the day portion of the date is imputed

M='Month': indicates that the month and day portions of the date are imputed
 Y='Year': indicates that the entire date (year, month, and day) is imputed

Example of Date Variables: Date of new anti-cancer therapy
 NEWCTXD_ - character date variable
 NEWCTXDT - numeric date variable
 NEWCDTFL - flag variable

Details on imputing partial dates for specific datasets are outlined below.

Adverse Events (AE):

Imputations in AE are used for slotting events to the appropriate study time periods and for sorting in data listings.

Dataset	Date	Missing Element	Rule
Adverse Events (AE)	Start Date	day, month, and year	
 • No Imputation for completely missing dates

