		day, month	
 • If study treatment start date is missing (i.e. subject did not start study treatment), then set start date = January 1. • Else if study treatment start date is not missing: 
 ○ If year of start date = year of study treatment start date then 
 • If stop date contains a full date and stop date is earlier than study treatment start date then set start date = January 1. • Else set start date = study treatment start date. ○ Else set start date = January 1.
		day	
 • If study treatment start date is missing (i.e. subject did not start study treatment), then set start date = 1st of month. • Else if study treatment start date is not missing: 
 ○ If month and year of start date = month and year of study treatment start date then 
 • If stop date contains a full date and stop date is earlier than study treatment start date then set start date= 1st of month. • Else set start date = study treatment start date. ○ Else set start date = 1st of month.
	End Date		
 • No imputation for partial end dates will be performed

Anti-Cancer Therapy (CTX) and Radiotherapy (RADIO):

Start and end dates are generally not imputed. If start or end dates need to be imputed for an analysis (e.g. to calculate duration or elapsed time as covariates for efficacy analyses), the rules for imputation will be defined within the algorithm of the derived covariate. Additionally, post treatment CTX and RADIO start dates may be imputed to determine date of new anti-cancer therapy. In this case only, NEWCTXDT (not all CTX and RADIO start dates) will be stored on appropriate efficacy datasets. Imputed partial dates will not be used to derive ATMPCTX (time since most recent prior therapy). In addition, the CTXTRTCD variable, and not any variables which use imputed partial dates, will be used to differentiate prior and follow-up CTX and RADIO.

Dataset	Date	Missing Element	Rule
Anti-Cancer Therapy (CTX) Radiotherapy (RADIO)	Start Date	day, month, and year	No Imputation for completely missing dates
		day, month	If partial date contains a year only set to January 1st.
		day	If partial date contains a month and year set to the 1 st of the month.
	End Date		No imputation for partial end dates will be performed

Surgery:

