All AEs of special interest will be summarized by categories of AE of special interest, preferred term and maximum toxicity grade in one table per treatment regimen (dabrafenib monotherapy, trametinib monotherapy, and dabrafenib plus trametinib combotherapy). AEs of special interest will be sorted by categories and then by preferred term in descending order based on incidence.

The following displays will be provided for selected AEs of special interest occur in > 5 subjects per treatment regimen:

- Summary of characteristics of AE of special interest, which will summarize event characteristics (serious, study treatment-related, fatal), number of occurrences, number of subjects, maximum toxicity, outcome, and action taken. The worst case approach will be applied at subject level for the event outcome and maximum grade, i.e. a subject will only be counted once as the worst case from all the events experienced by the subject. For action taken to a event, subject will be counted once under each action, e.g. if a subject has a event leading to both study treatment discontinuation and dose reduction, the

subject will be counted once for study treatment discontinuation and dose reduction, respectively.

- Summary of onset and duration. Time to onset (days) and duration of first occurrence (days) will be summarized. In addition to descriptive statistics (mean, median, min, max), time to onset will be summarized in categories of 0-2 weeks, >2-4 weeks, >4-8 weeks, >8-12 weeks, >12-18weeks, >18-24 weeks, and >24 weeks, and duration of first occurrence will be summarized in categories of 1-5 days, 6-10days, >10 days.
- Cumulative incidence plot.

Listing will be provided which profiles all categories of AEs of special interest per treatment regimens. Other AEs of special interest may be added later. Depending on the number of events, summary and/or listing may be provided appropriately.

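### First occurrences of adverse events of special interest still ongoing at cut-off have no duration under the SAP's rules, so the reported durations are biased short on average.

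*SAP*

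**What the plan says.** SAP 12.3 sets the display: "Time to onset (days) and duration of first occurrence (days) will be summarized". Besides the descriptive statistics, "duration of first occurrence will be summarized in categories of 1-5 days, 6-10days, >10 days". There is no band or row for events that have not ended. The trigger is low: "The following displays will be provided for selected AEs of special interest occur in > 5 subjects per treatment regimen". The results go into Tables 3.1611 (dabrafenib monotherapy), 3.1711 (trametinib monotherapy) and 3.1811 (combination).

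Four other SAP rules decide what happens to an event without a stop date:

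- Section 9.2.4: "Durations (e.g., the duration of an adverse event, duration of exposure, etc.) are calculated as the stop date minus the start date plus one".
- Section 9.2.5, on partial dates in general: "Imputed partial dates will not be used to derive study day, duration (e.g. duration of adverse events), or elapsed time variables".
- Section 9.2.5, adverse event end dates: "No imputation for partial end dates will be performed".
- Section 9.1: "Consequently, there will be no imputation for missing data".

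On timing, section 4.2 says: "The final analysis will be performed after the last patient has the week 16 efficacy assessment". Treatment itself continues until progression, death or unacceptable toxicity (SAP section 3).

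**The concern.** The analysis is timed while some patients will still be on treatment, so some adverse events will be open at cut-off. Section 9.2.6 recognises this for dosing records: an exposure end date missing at cut-off is set to the earliest of cut-off, withdrawal and death. PFS and duration of response are censored (13.3.1, 13.3.2). Adverse event duration is the same kind of open interval, and the SAP gives it no rule.

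An event is more likely to be open at cut-off if it lasts long. Summarising only events with a stop date therefore under-represents long ones. The safety profile is a secondary objective, and several listed events of special interest (skin events, hypertension, oedema, cardiac events) can persist. For those, the table could make toxicity look briefer than it was. With as few as six subjects behind a summary, one or two lost events can move the median.

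**Working it through.** **Tracing the rules.** The plan states no figure for event duration, so there is none to reproduce. Take a first occurrence that started on a known date and has not ended. Section 9.2.4 needs a stop date; there is none. Section 9.2.5 imputes no adverse event end date and keeps imputed dates out of durations. Section 9.1 imputes nothing. The duration is therefore missing. Section 12.3 has nowhere to put a missing duration, so the event falls out of the mean, median, minimum, maximum and all three bands.

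**A six-subject example (invented values).** Four events resolved after 4, 6, 8 and 12 days; two are ongoing at 60 and 80 days.

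- Resolved only: mean (4+6+8+12)/4 = 7.5; median 7; above 10 days 1/4 = 25%.
- All six: median (8+12)/2 = 10; above 10 days 3/6 = 50%; mean at least (4+6+8+12+60+80)/6 = 28.3.

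**Size under assumed inputs.** Let durations be exponential with median m, so λ = ln 2/m. Let every patient be cut off at day F = 112 (16 weeks), with onset uniform over 0 to F.

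- Share ongoing = (1 − e^(−λF))/(λF). For m = 30: λ = 0.0231, λF = 2.588, share = (1 − 0.0752)/2.588 = 35.7%.
- Share resolved with duration at most d = (1 − e^(−λd)) − [(1 − e^(−λd))/λ − d·e^(−λd)]/F. At d = 18.5 this is 0.348 − (15.05 − 12.07)/112 = 0.321. Divided by the resolved share 0.643, it gives 0.50, so the reported median is about 18.5.

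Simulation extends this to other cut-offs and onsets. Each cell shows the percentage ongoing, then the reported median in days.

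| Cut-off and onset (assumed) | True median 5 | True median 30 | True median 60 |
|---|---|---|---|
| All at day 112; onset uniform to cut-off | 6%; 4.7 | 36%; 18.5 | 56%; 24 |
| Spread over days 112–365; onset uniform to cut-off | 3%; 4.8 | 20%; 24 | 36%; 37 |
| Spread over days 112–365; onset in days 0–112 | 0.2%; 5.0 | 6%; 27.6 | 18%; 46 |
| Spread over days 112–365; onset in days 0–56 | under 0.1%; 5.0 | 3%; 28.9 | 12.5%; 50 |

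In the first row with a true median of 30, the share above 10 days falls from 79% to 69%; in the third row it is 78%. Log-normal durations (log-scale SD 1.2) give similar medians: 18.1 and 26.3 in the first row, 25.7 and 43.0 in the third. Kaplan-Meier with ongoing events censored recovers 30.1 and 59.8 in the first row.

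**Combination phase.** Arms A and B normally start the combination in week 9, so the last patients enrolled there have about 16 − 8 = 8 weeks on it at the earliest cut-off. With F = 56 and a true median of 30, 56% are ongoing and the reported median is 12.2. This describes only those patients, not Table 3.1811 as a whole.

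**The case against.** The strongest reply is that exclusion is inferred. The end-date sentence in 9.2.5 is about partial dates, not ongoing events. Section 9.2 refers to separate dataset specifications, and the three tables follow a sponsor display standard (ESI2A). Neither is available here, and either could hold a rule. This stands as a caution, but the SAP's own rules, read together, leave an ongoing event without a duration.

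Unresolved events may also be visible elsewhere. The characteristics tables in 12.3 report event outcome, worst case per subject, under the same trigger, and listings are planned. A reader might infer that the report as a whole will present these toxicities as more reversible than they are; the documents do not support going that far. What remains is that neither display corrects the duration statistics.

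The 16-week figures are a worst case for total follow-up. Week 16 is the last patient's assessment; earlier patients have longer. First events on monotherapy mostly start in the first eight weeks and have more time to resolve, as the last table row shows.

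Some persistent toxicities may not reach the display. With 54/3 = 18 per arm and the trametinib phase III rates in protocol 1.1.2, expected counts are 0.07 × 18 = 1.3 for ejection-fraction decrease and 0.26 × 18 = 4.7 for oedema, against a trigger of six. Rash (0.57 × 18 = 10.3) and diarrhoea (0.43 × 18 = 7.7) would qualify, and the combination regimen draws on up to 54 patients. Those rates cover a full trial, not eight weeks.

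Three further inferences should be resisted. Exposure is not the only record with end-date imputation: 9.2.5 also covers concomitant medications, blood products and prior therapies, though only for partial dates. Not every ongoing event is a long one, since one may start just before cut-off. And the mechanism is right truncation, not length bias, which usually means over-sampling of long durations.

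**Conclusion.** The point holds. For adverse events open at cut-off the SAP has no duration rule, and its existing rules imply that they leave the duration summaries. The bias is downward on average.

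Its size cannot be read from the documents. Under exponential durations, a true 30-day median is reported as about 18.5 at worst and 24 to 29 with cut-offs spread over days 112 to 365; a true 60-day median as about 24, and 37 to 50. At a true median of 5 days the loss is at most about 0.3 days in these scenarios. The duration distribution, onset pattern and spread of cut-offs are all assumptions, so a reader should not take any one of these figures as the expected error.

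This is a minor-to-moderate weakness in secondary, descriptive safety tables. The primary p-ERK endpoint is not touched.

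**What to change.** In SAP 12.3, for Tables 3.1611, 3.1711 and 3.1811:

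1. Print the number of first occurrences ongoing at cut-off beside the duration statistics.
2. Count ongoing events that have already lasted more than 10 days in the top band, and show shorter ongoing events in a row of their own.
3. Give the median and quartiles by Kaplan-Meier, censoring events without a stop date at the earlier of last contact and data cut-off.
4. Label any mean or maximum that is kept as resolved events only.

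The cost is SAP wording and a Kaplan-Meier step in three tables, with no new data. The downside is that with few events the median may be imprecise or not reached. Censoring at last contact may also be informative when contact ends through death or withdrawal. If Kaplan-Meier is thought too much for six events, items 1, 2 and 4, with the resolved-only label extended to the median, would still stop the table being misread. If the dataset specifications or display standard already hold a rule, it should be stated in 12.3.

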12.4. Deaths and Serious Adverse Events

In the event that a subject has withdrawn consent, no data after the withdrawal of consent date from this subject including death is supposed to appear in the database, which should be part of the data cleaning process. All deaths occurring any time from the time of informed consent to the clinical cut-off date will be summarised based on the number and percentage of subjects. This summary will classify subjects by time of death relative to the last dose of medication (> 30 days or ≤ 30 days) and primary cause of death (disease under study, SAE related to study treatment, or other). A supportive listing will be generated to provide subject-specific details on subjects who died.

All SAEs will be tabulated based on the number and percentage of subjects who experienced the event. Separate summaries will also be provided for study treatment-related SAEs and fatal SAEs. The summary tables will be displayed in descending order of total incidence first and then by each treatment arm for each PT term.

A study treatment-related SAE is defined as an SAE for which the investigator classifies the relationship to study treatment as “Yes”. A worst case scenario approach will be taken to handle missing data, i.e. the summary table will include events with the relationship to study treatment as ‘Yes’ or missing.

SAEs are included in the listing of all adverse events. Separate supportive listings with subject-level details will be generated for:

- Fatal SAEs
- Non-Fatal SAEs.
- Another summary will be included which summarizes the number of subjects with serious AE, total number of exposed subjects, number of serious AEs, number of drug-related serious AEs, number of fatal serious AEs, and number of drug-related fatal serious AEs, for any European submissions.

12.5. Adverse Events Leading to Discontinuation of Study Treatment and/or Withdrawal from the Study and Other Significant Adverse Events

The following categories of AEs will be summarized separately in descending order of total incidence first and then by each treatment arm for each PT term, and separate supportive listings will be generated with subject level details for those subjects:

- AEs Leading to Discontinuation of Study Treatment
- AEs leading to Withdrawal from the Study
- AEs Leading to Dose Interruptions
- AEs Leading to Dose Reductions

12.6. Pregnancies

While pregnancy itself is not considered to be an AE or SAE, any pregnancy complication or elective termination of a pregnancy for medical reasons will be recorded as an AE or SAE as described in the protocol. If subjects and subjects' spouse become pregnant while on the study, the information will be included in the SAE narratives and no separate table or listing will be produced.

12.7. Clinical Laboratory Evaluations

The assessment of laboratory toxicities will examine the following laboratory tests:

Hematology: Hemoglobin (HGB), White Blood Cell (WBC) count, and Platelet count. Automated WBC differential (expressed as absolute count) for basophils, eosinophils, lymphocytes, monocytes, and total neutrophils.

Clinical Chemistry: Sodium, Potassium, Calcium, Albumin, Total Protein, Blood Urea Nitrogen (BUN), Creatinine, Estimated Creatinine Clearance, Lactate Dehydrogenase (LDH), Gamma-Glutamyl Transpeptidase (GCT), phosphate, and C-Reactive Protein (CRP). BUN, LDH, CRP, Total Protein, and Estimated Creatinine Clearance are not gradable by CTCAE v4.0. For Sodium, Potassium, and Calcium, two bi-directional parameters (hyper and hypo), the tests will be graded by CTCAE v4.0 in both directions.

Liver Function Tests: Aspartateaminotransferase (AST) or Serum Glutamic Oxaloacetic Transaminase (SGOT), Alanine aminotransferase (ALT) or Serum Glutamic Pyruvic Transaminase (SGPT), Alkaline phosphatase, Total bilirubin (total) and Direct bilirubin (only recorded when Total bilirubin $\geq 2 \times$ ULN). All these tests are gradable by CTCAE v4.0.

Coagulation Tests: Prothrombin time (PrT), International Normalized Ratio (INR), and Activated Partial thromboplastin time (aPTT). All tests at screening only.

Laboratory grades will be reported using the Common Terminology Criteria for Adverse Events (CTCAE v4.0).

Summary of lab values and change from baseline by scheduled visits using mean, median, standard deviation, minimum and maximum will be provided.

Summaries of lab data by maximum toxicity grade will be provided.

Coagulation tests are only collected at baseline. Therefore this/these test(s) will not appear in any summaries of changes from baseline.

Summaries of worst case grade increase from baseline grade will be provided for all the lab tests that are gradable by CTCAE v4.0. These summaries will display the number and percentage of subjects with a maximum post baseline grade increasing from their baseline grade. Any increase in grade from baseline will be summarized along with any increase to a maximum grade of 3 and any increase to a maximum grade of 4. Missing baseline grade will be assumed as grade 0. In addition, the summary will include grade increase from baseline by scheduled visits. For laboratory tests that are graded for both low and high values, summaries will be done separately and labeled by direction, e.g. sodium will be summarized as hyponatremia and hypernatremia.

For lab tests that are not gradable by CTCAE v4.0, summaries of worst case changes from baseline with respect to normal range will be generated. Decreases to low, changes to normal or no changes from baseline, and increases to high will be summarized at each scheduled visit as well as for the worst case post baseline. If a subject has a decrease to low and an increase to high during the same time interval, then the subject is counted in both the “Decrease to Low” categories and the “Increase to High” categories. In addition, the summary will include worst case changes from baseline with respect to normal range by scheduled visits.

Separate summary tables for hematology, chemistry, liver function, and coagulation, laboratory tests will be produced.

Detailed derivation of baseline assessment is specified in Section 9.2.

Unless otherwise specified, the denominator in percentage calculation at each scheduled visit will be based on the number of subjects with non-missing value at each particular visit.

